9.7.1.1.3 EXPLORATORY ENDPOINTS

The exploratory endpoints of the study are:

- Time to change of concomitant AD treatment (ie, dose increase and/or initiation of treatment with AChEI or memantine after randomization) by 24 months
- The proportion of subjects at 24 months who received dose increases and/or initiation of treatment with AChEI or memantine after randomization
- The rate of change over time (mean slope) based on NPI-10 item score over 24 months
- Change from baseline in NPI-10 item at 24 months

- Change from baseline in EQ-5D (subject self-reported, study partner self-reported, and subject measured by proxy) and QOL-AD (subject and study partner) at 24 months
- Change from baseline in Zarit's Burden Interview at 24 months

9.7.1.1.4 BIOMARKERS ENDPOINTS

The biomarker endpoints for this study are:

- Change from baseline in amyloid PET SUVR composite at 24 months for brain amyloid levels
- Change from baseline in CSF biomarkers t-tau and p-tau at 24 months
- Change from baseline in CSF amyloid biomarkers A β (1-40), A β (1-42), and A β (1-x) at 24 months
- Change from baseline in total hippocampal volume at 24 months using vMRI
- Change from baseline in the preservation of connectivity on fMRI at 24 months

9.7.1.2 Definitions of Analysis Sets

- The Randomized Set is the group of subjects who are randomized to study drug.
- The Safety Analysis Set is the group of subjects who receive at least 1 dose of study drug and have at least 1 postdose safety assessment.
- The Full Analysis Set (FAS) is the group of randomized subjects who receive at least 1 dose of study drug and have baseline and at least 1 postdose primary efficacy measurement.
- The Per Protocol Analysis Set (PPS) is the subset of subjects in the FAS who sufficiently comply with the protocol. The PP Analysis Set will be used to conduct a sensitivity analysis of the primary efficacy endpoint. Details of the evaluability criteria will be determined before database lock and treatment unblinding, and will be specified in the statistical analysis plan.
- The PK Analysis Set is the group of subjects with at least 1 quantifiable elenbecestat (E2609) plasma concentration with a documented dosing history.
- The PD Analysis Set is the group of subjects who have sufficient PD data to derive at least 1 PD parameter.

9.7.1.3 Subject Disposition

The number of subjects screened, the number (percent) of subjects who failed screening, and the reasons for screen failure will be summarized, based on data reported on the Screening Disposition eCRF. The distribution of the number of randomized subjects enrolled by each site will be summarized for each randomized treatment group. The primary reasons for

screen failures (did not meet inclusion or met exclusion criteria, AE, lost to follow-up, withdrawal of consent, and other) will be presented.

Study Completion: the number (percent) of randomized and treated subjects who completed the study and who discontinued from the study will be summarized according to the primary reason for discontinuation and secondary reason(s) for discontinuation, based on data reported on the Subject Disposition (Study Phase) CRF. The number (percent) will be presented by treatment group and total for subjects; randomized, not treated, treated, who completed the study, and discontinued from the study. The primary reasons for early withdrawal from the study are: AE, lost to follow-up, subject choice, withdrawal of consent, pregnancy, study terminated by sponsor, and other. The secondary reasons for early withdrawal from the study are: AE, subject choice, and other.

Completion of Study Treatment: the number (percent) of randomized and treated subjects who completed study drug and who discontinued from study drug will be summarized according to the primary reason for discontinuation and also according to secondary reason(s) for discontinuation, based on data reported on both the Subject Disposition (Study Phase) eCRF and ED from Study Drug eCRF. The number (percent) will be presented by treatment group and total for subjects; randomized, not treated, treated, who completed study drug, and discontinued from study drug. The primary reasons for early discontinuation from the study drug are: AE, subject choice, pregnancy, inadequate therapeutic effect, and other. The secondary reasons for early discontinuation from the study drug are: AE, subject choice, inadequate therapeutic effect, and other.

9.7.1.4 Demographic and Other Baseline Characteristics

Demographic and other baseline characteristics for the Safety Analysis Set and FAS will be summarized for each treatment group using descriptive statistics. Continuous demographic and baseline variables include age, CDR scores, ADAS-cog₁₄, MMSE and FAQ; categorical variables include sex, age group (equal or less than 65 years, age greater than 65 years), race, ethnicity, region, *ApoE4* genotype, prior treatment with AChEIs or memantine (no or yes), and clinical subpopulation (MCI due to AD or the early stages of mild AD).

9.7.1.5 Prior and Concomitant Therapy

All investigator terms for medications recorded in the eCRF will be coded to an 11-digit code using the World Health Organization Drug Dictionary (WHO DD) (Mar 2014). The number (percentage) of subjects who took prior and concomitant medications will be summarized on the Safety Analysis Set by treatment group, Anatomical Therapeutic Chemical class, and WHO DD preferred term (PT). Prior medications will be defined as medications that stopped before the first dose of study drug. Concomitant medications will be defined as medications that (1) started before the first dose of study drug and were continuing at the time of the first dose of study drug, or (2) started on or after the date of the first dose of study drug up to the date of the last dose. All medications will be presented in subject data listings.

Medications taken within the 12-week Follow-Up Period will also be recorded.

9.7.1.6 Efficacy Analyses

The FAS will be used as the primary population for all efficacy analyses, while the PPS will be used as the supportive population.

9.7.1.6.1 PRIMARY EFFICACY ANALYSIS

The primary analysis will be based on an intent to treat philosophy without regard to adherence to treatment. The primary analysis of the change from baseline in CDR-SB at 24 months will be performed to compare elenbecestat (E2609) 50 mg per day versus placebo using a linear mixed effects model for repeated measures (MMRM) on the FAS. The MMRM model will include baseline CDR-SB as a covariate, with treatment group, visit, randomization stratification variables (ie, region [7 levels], clinical dementia [yes, no], and concurrent AD medication use at randomization (Visit 2) [yes, no]), and treatment group-by-visit interaction as fixed effects. An unstructured covariance matrix will be employed to model the covariance of within subject effect; if MMRM fails to converge then a covariance structure with fewer parameters from the following list will be employed according to the prespecified order in the list until the MMRM converges. The list of covariance structure will include Heterogeneous Toeplitz, Toeplitz, Heterogeneous Compound Symmetry, and Compound Symmetry. This primary analysis will include all observed post baseline data of the change from baseline in CDR-SB without imputation of missing values. The treatment effect for elenbecestat (E2609) versus placebo will be compared at 24 months based on MMRM model. The LS means and difference in LS means between elenbecestat (E2609) treatment group and placebo, and corresponding 95% CI will be presented.

The null hypothesis is that there is no difference in the mean change from baseline in CDR-SB at 24 months between elenbecestat (E2609) 50 mg per day and placebo. The corresponding alternative hypothesis is that there is a difference in the mean change from baseline in CDR-SB at 24 months between elenbecestat (E2609) 50 mg per day and placebo.

The primary analysis will be repeated to minimize the impact of change in concomitant AD medications where efficacy data after initiation of new AD medications and increase of current AD medications will be censored.

The following sensitivity analysis will be conducted to evaluate the impact of missing data: the primary endpoint will be analyzed using ANCOVA after multiple imputation. The ANCOVA model will include baseline CDR-SB as a covariate, with treatment group and randomization stratification variables as factors.

Subgroup analysis (eg, *ApoE4* genotype) and additional sensitivity analysis for the primary endpoint will be performed as appropriate.

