The CDR will be conducted every 3 months during the Core Study; other cognitive and functional assessment instruments will be administered every 6 months. Every 3 months, the investigator is required to confirm the clinical staging of AD (ie, dementia or nondementia). This staging decision will be verified via a central review process and adjudicated if necessary (adjudication will only occur when there is a discrepancy between the clinical disease staging made by the site compared to that determined by the central review process; moreover, where adjudication is required, it will be undertaken by an independent assessor(s)).

The health-related quality of life measures will be conducted every 6 months during the Core Study, along with the NPI-10.

MRI scans (including vMRI and fMRI) will be performed at 12 and 24 months during the Core Study or at the ED visit.

At every visit, AEs will be assessed, concomitant medications will be reviewed, physical examinations with dermatologic review by the study investigator will be performed, vital signs and respiratory rate will be measured, suicidality will be assessed, blood will be drawn for clinical chemistry, hematology, and for immunologic assessments. A urine sample will be provided for dipstick urinalysis. Other assessments, including safety assessments (neurologic exams, ECGs, urine pregnancy tests for females of child-bearing potential), and blood draws for PK, PD and assessment of immune status are performed at different intervals throughout the treatment period of the study.

For subjects who consent to the amyloid PET longitudinal substudy, amyloid PET will be conducted after 12 and 24 months of treatment during the Core Study (or at the ED visit, provided the subject has received at least 39 weeks of study drug). For subjects who consent to the CSF longitudinal substudy, CSF will be collected after 24 months of treatment during the Core Study (or at the ED visit, provided the subject has received at least 39 weeks of study drug). Note that subjects who are assessed by both amyloid PET and CSF A β (1-42) are required to wait for a minimum of 48 hours between the 2 procedures. (revised per Amendment 01) Please refer to Schedule of Assessments ([Table 3](#)).

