The other continuous secondary efficacy endpoints as defined above will be analyzed using the same MMRM model as the primary efficacy analysis to compare elenbecestat (E2609) 50 mg per day versus placebo on the FAS, using baseline value corresponding to the response variable in the model.

The relationship between clinical changes at 24 months (CDR-SB, ADAS-cog₁₄, MMSE, and FAQ) and changes in each of the biomarkers (amyloid PET, CSF t-tau and p-tau, vMRI, and fMRI) at 24 months, will be evaluated using an ANCOVA model. Changes in clinical scales at 24 months will be the response variables and either continuous or categorical change of biomarkers will be independent variables. The ANCOVA model will also include baseline value for clinical scale as a covariate, randomization stratification variables, treatment group as factors, and other terms as appropriate.

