9.7.2 Determination of Sample Size

The sample size for this study is estimated based on comparison of elenbecestat (E2609) versus placebo with respect to the primary efficacy endpoint, the change from baseline CDR-SB at 24 months. Based on available ADNI data [amyloid positive, MMSE equal or greater than 24, late MCI (global CDR=0.5) populations from ADNI, ADNI 2 and ADNI GO] the mean and the standard deviation of the change from baseline in the CDR-SB at 24 months in the placebo group are assumed to be 1.75 and 2.05, respectively. Therefore, assuming a 25% reduction in the mean change from baseline CDR-SB at 24 months for the elenbecestat (E2609) 50 mg per day dose group compared to placebo with a common standard deviation of 2.05 and an estimated 30% dropout rate in this study, a total sample size of 1330 subjects, 665 subjects in each treatment group, will be required to detect the treatment difference between elenbecestat (E2609) 50 mg per day and placebo using a 2-sample t-test with 90% power at a significance level of 2-sided alpha =0.05.

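### The primary MMRM, as written, fits one baseline CDR-SB slope and one dementia offset for all visits, and so may recover only part of the precision available at month 24

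*Protocol*

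**What the plan says.** Section 9.7.1.6.1 (repeated in the Synopsis) lists the terms of the primary model: "The MMRM model will include baseline CDR-SB as a covariate, with treatment group, visit, randomization stratification variables" (region, clinical dementia yes/no, concurrent AD medication yes/no), "and treatment group-by-visit interaction as fixed effects". No other interaction is named. On the covariance it says: "An unstructured covariance matrix will be employed to model the covariance of within subject effect", with Heterogeneous Toeplitz, Toeplitz, Heterogeneous Compound Symmetry and Compound Symmetry as ordered fallbacks. The treatment effect "will be compared at 24 months based on MMRM model".

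Section 9.1.2.1 gives the schedule: "The CDR will be conducted every 3 months during the Core Study". That makes eight on-treatment post-baseline visits, months 3 to 24.

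Section 9.7.1.6.2 reuses the same model for the other continuous secondary endpoints, "using baseline value corresponding to the response variable in the model".

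Section 9.7.2 sizes the trial with an unadjusted two-sample t-test; the mean and SD of the 24-month change in the "placebo group are assumed to be 1.75 and 2.05, respectively".

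**The concern.** The response is change from baseline, which is zero at time zero. If more impaired subjects progress faster, their extra decline has to widen with time, so the baseline slope and the dementia offset should be small at month 3 and largest at month 24. The protocol itself treats progression as stage-dependent: section 7 expects 18 months of treatment to be enough in mild to moderate disease but asks for longer in prodromal disease. A second force acts the other way early on. Rating error at baseline enters every change score with a negative sign, which can make the early slope negative.

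A model with one slope must compromise across visits. Generalised least squares with an unstructured covariance weights by precision, and change scores at early visits vary least. The fitted slope then sits near its early value, and the month-24 residual keeps much of the variance that baseline could have explained. At stake is precision at the trial's single decision point, from data that are collected anyway.

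**Working it through.** **The plan's own figure.** Effect = 0.25 × 1.75 = 0.4375; SD 2.05; two-sided alpha 0.05; power 0.90. Per arm, n = 2(1.960 + 1.2816)² × 2.05² / 0.4375² ≈ 462. With 30% dropout, 462 / 0.7 = 660 per arm, 1320 in total, close to the stated 1330. At 665 × 0.7 = 465.5 per arm, power = Φ(0.4375 / (2.05 × √(2/465.5)) − 1.96) = 0.902. This reproduces the plan and takes no credit for baseline adjustment.

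**Assumptions not in the protocol.** It gives no baseline SD, no baseline-to-change correlation, no SD by visit and no decline by stratum. I therefore assume:
- R², the share of month-24 variance explained by baseline, is 5, 10 or 15%.
- The baseline effect per baseline SD grows linearly from zero: β(t) = β₂₄u, with u = t/24.
- The SD of change at month 3 is 0.8 to 1.0.
- The residual covariance S is a random slope or a random walk, plus independent visit noise.

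**Formulas.** The large-sample common slope is b = (1′S⁻¹β) / (1′S⁻¹1). The month-24 residual variance is S₂₄ + (β₂₄ − b)² with a common slope and S₂₄ with a slope per visit. The share of the attainable gain kept is 1 − (β₂₄ − b)²/β₂₄².

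**Worked case: R² = 10%, random slope, month-3 SD 0.8.**
- β₂₄ = √0.10 × 2.05 = 0.648; S₂₄ = 4.2025 − 0.4203 = 3.782.
- S = a·uu′ + c·I must give 3.782 at month 24 and 0.64 − (0.648/8)² = 0.633 at month 3. So a = (3.782 − 0.633)/(1 − 1/64) = 3.199 and c = 0.583.
- Over eight visits Σu = 4.5 and Σu² = 3.1875, so c + aΣu² = 10.78.
- 1′S⁻¹u is proportional to 4.5 × 0.583/10.78 = 0.2436. 1′S⁻¹1 is proportional to 8 − 3.199 × 4.5²/10.78 = 1.991.
- b = (0.2436/1.991) × 0.648 = 0.079, against 0.648 needed.
- Month-24 variance = 3.782 + 0.569² = 4.106, a ratio of 1.086; 23% of the gain is kept. Power is 0.909, against 0.929 with a slope per visit.

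**Across the assumed covariances (linear growth):**

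| R² | Month-24 variance inflated by | Power, common slope | Power, slope per visit |
|---|---|---|---|
| 5% | 3–4% | 0.906–0.908 | 0.916 |
| 10% | 7–9% | 0.909–0.914 | 0.929 |
| 15% | 10–13% | 0.913–0.920 | 0.942 |

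At R² = 10% the fitted slope is 0.08 to 0.15. Over these and similar covariance shapes about 20 to 50% of the gain is kept; stronger correlation among early residuals lowers the share.

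**Other shapes of the baseline effect.**
- Constant over visits: b = β₂₄, so nothing is lost.
- Linear growth with equal visit weights, as under the compound-symmetry fallback: b = (4.5/8)β₂₄ = 0.5625β₂₄, so 1 − 0.4375² = 81% is kept.
- Early regression to the mean (assumed slope −0.25 at month 3, rising linearly, R² = 10%): b is negative. With b = −0.154 the variance is 3.782 + 0.802² = 4.426 and power 0.887; over the covariances tried, power is 0.874 to 0.887, below the 0.902 of no adjustment.

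**Dementia offset.** An assumed 1-point stratum difference at month 24, with a 25% share, explains 0.25 × 0.75 / 4.2025 = 4.5% of the variance.

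**Simulation of the MMRM** (N = 1330, 30% monotone dropout, correlation 0.3, 1-point stratum difference, 60 replicates). The common slope was 0.095 against a true 0.615 and the offset 0.15 against 1.0. Model standard errors were 0.1216 with no adjustment, 0.1197 with common terms and 0.1135 with by-visit terms. The mean treatment estimate was −0.450 under all three. With baseline-dependent dropout the estimates were −0.434, −0.434 and −0.433.

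**The case against.** The strongest reply is that the size of the loss comes from assumptions and not from the protocol. That stands: with a constant baseline effect nothing is lost, and under compound symmetry most of the gain survives. A reader might infer that baseline adjustment does almost nothing at month 24. The text does not support that, since even the linear-growth cases keep a fifth to a half of the gain.

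A reader might also infer that the trial is underpowered. It is not, on its own terms: 1330 rests on an unadjusted t-test and reproduces at 0.902, and the linear-growth cases stay above 0.90. Only the assumed regression-to-the-mean cases fall below. Nor is there evidence of a biased comparison; the simulated estimates agree closely, although 60 replicates are too few to judge type I error.

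Entry criteria restrict baseline range (global CDR 0.5, MMSE at least 24, section 9.3.1) and cap the dementia stratum at about 25% (section 9.3). This makes the 15% case less likely. The planned ANCOVA after multiple imputation has a slope specific to month 24 and could reveal a problem, but as a sensitivity analysis it leaves the primary test unchanged.

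For the secondary scales, Table 3 schedules treatment visits only at months 6, 12, 18 and 24. The figures above do not carry over to them.

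**Conclusion.** The point holds as a conditional one about precision. The stated model constrains the baseline slope and the dementia offset to be equal at all visits although the test is at month 24. If their effect on change grows over time, the first-choice unstructured fit recovers roughly 20 to 50% of the attainable variance reduction. That costs about 1 to 3 power points for R² of 5 to 15%; at 10%, about 0.91 against 0.93. Under assumed early regression to the mean the adjustment can be worse than none. All of this rests on the assumed growth pattern and visit-wise variances. It is worth correcting because the remedy is cheap, not because the design fails without it.

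**What to change.** Before unblinding, add baseline CDR-SB-by-visit and clinical dementia (yes/no)-by-visit to the fixed effects in section 9.7.1.6.1 and the Synopsis, and the matching baseline-by-visit term to the secondary MMRMs in section 9.7.1.6.2. The gain for the secondary endpoints was not computed. If the SAP already carries these terms, align the protocol wording with it.

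The cost is wording plus 7 + 7 = 14 further parameters in the primary model, against about 0.7 × 1330 = 931 completers. No new data or subjects are needed, and the sample-size statement can stay as it is.

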9.1.2.1 Treatment Period

During Visit 2, the following assessments will be completed before the subject receives their first dose of study drug: MMSE, CDR, ADAS-cog₁₄, FAQ, and NPI-10. These assessments will provide baseline measurements for the study. Inclusion and exclusion criteria will again be reviewed together with concomitant medications and assessment of AEs. A single 12-lead ECG will be conducted. All ECG recordings will be evaluated by a central reader. The Columbia-Suicide Severity Rating Scale (C-SSRS) will also be administered. A baseline routine physical examination with dermatologic review, vital signs measurements, clinical laboratory testing (including viral characterization), urinalysis using urine dipstick, and a urine pregnancy test (females of child-bearing potential only), will be performed. Additional blood samples will be taken for immunologic assessments. Some of the immunologic assessment blood sample will be used to prepare isolated peripheral blood mononuclear cells (PBMCs) which will be stored for later testing. The results of some of the immunologic assessments will be provided to the DSMB for periodic review during the study. Whilst there is no prescribed order in which the assessments at each visit are to be performed, the subject component of the cognitive, functional and quality of life assessments are to be performed in the morning whenever possible, or consistently at the same time of the day and ideally should be completed before the more invasive procedures (eg, physical examination, ECG, blood draw).

Subjects will be randomized at Visit 2 (Day 1) to receive elenbecestat (E2609) 50 mg per day or placebo administered orally QD in the morning with or without food. Subjects will be encouraged to stay at the site for an appropriate period of time for observation following their first dose of study drug. Double-blinding to study drug will be in effect throughout the Treatment Period.

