9.2.3 Rationale for Clinical Endpoints

The CDR is a clinical global rating scale requiring the interviewing of both the subject and a study partner who knows and has contact with the subject. The CDR is a clinician directed assessment of both cognition and function, and is intended to capture the state and therefore the disease stage of the individual. The CDR has been proposed as an acceptable approach for following disease progression and confirming treatment effects in AD. The cumulative score or CDR-SB is a well-described, validated, and reliable measure of change through the course of AD and has been proposed as a suitable single outcome measure for AD trials in dementia and pre-dementia populations (FDA 2013 AD Guidelines, EMA 2016 AD Guidelines).

The ADAS-Cog is the most widely used cognitive scale in AD clinical studies (Rosen, et al., 1984). The 14-item version will be used in the present study since it is considered more sensitive for less impaired populations such as MCI/Prodromal and mild AD subjects (Fleisher, et al., 2007). Furthermore, a separate endpoint for the ADAS-cog₁₄ immediate recall and delayed recall subtests is included.

The MMSE is a cognitive instrument commonly used for screening purposes, for staging of disease severity and is often measured longitudinally in AD clinical studies to follow disease progression and treatment effects (Folstein, et al., 1975).

The FAQ collects information on 10 items concerned with performing daily tasks necessary for independent living. The FAQ is considered as a better indicator of clinical meaningfulness than cognitive change as it reflects the subject's functional state and should correlate well with AD progression.

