9.5.1.4.2 PHARMACODYNAMIC, PHARMACOGENOMIC, AND OTHER BIOMARKER, ASSESSMENTS

Biomarkers

The CSF sample will be used for PD assessments including but not limited to CSF A β (1-x), A β (1-42), A β (1-40), t-tau, p-tau, and BACE1 levels and activity.

The plasma sample will be used for A β (1-x) analysis and may be used for exploratory biomarker analyses. A β (1-x) in both CSF and plasma will be measured using a modified commercially available enzyme-linked immunosorbent assay (ELISA). The prescreening and postscreening analysis of CSF A β (1-42), A β (1-40), t-tau, and p-tau will be performed using commercially available ELISAs. BACE1 levels will be measured using internally developed fluorescence resonance energy transfer and ELISA based assay(s). Substrates of BACE1 inhibition may also be explored using Western blots or other amenable methodology if clinical observations warrant and if analytes can be reliably tested in samples collected.

Blood samples will be collected for PD assessments as specified in [Table 2](#) and [Table 3](#). The blood sample collected for PD analyses at Screening should be collected at fasting or at least 2 hours after the most recent meal and PD blood samples should be taken predose at Visits 3, 4, 6, 7, 9, 11, and 13 (or ED) and, as far as is feasible, samples should be taken at the same time of day

Blood samples and CSF (if applicable) collected at Screening will be stored for determination of prior exposure to any suspected infective agents in the event that the subject develops TEAEs that warrant further investigation (eg, treatment-emergent infection). Testing may include, but not be limited to, serological tests (eg, HSV1 and 2), viral titer by quantitative polymerase chain reaction (Q-PCR), and/or human leukocyte antigen (HLA) genotyping.

For all subjects, baseline and on-study blood samples, DNA samples, and any collected CSF samples (if applicable) will be stored for up to 15 years.

See the laboratory manual (to be supplied to study sites) for a description of the collection, handling, and shipping procedures of the biomarker samples.

Pharmacogenomics

A blood sample will be obtained at Screening and will be used to determine the *ApoE* genotype of subjects enrolled in this study. The findings will be used in the statistical analysis to determine the effects on treatment response and safety.

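### The primary MMRM is valid and meets its stated power, but fixing it with only baseline CDR-SB and the strata forgoes possible precision from pre-dose variables the trial already collects

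*Protocol*

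**What the plan says.** Section 9.7.1.6.1 of the Protocol, repeated in the synopsis, lists the terms of the primary model: "The MMRM model will include baseline CDR-SB as a covariate, with treatment group, visit, randomization stratification variables". The strata are region, clinical dementia and concurrent AD medication, and the only interaction is treatment-by-visit. Baseline CDR-SB therefore has one coefficient for all visits. The protocol expressly leaves the order of the secondary tests and the per-protocol criteria to the statistical analysis plan. It does not do so for the covariate list.

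Other baseline data are collected anyway. Age comes with demography at Screening (9.5.1.1). At Visit 2, section 9.1.2.1 says "the following assessments will be completed before the subject receives their first dose of study drug: MMSE, CDR", and the same list goes on to ADAS-cog14 and FAQ. ApoE genotype is scheduled at Screening (9.5.1.4.2), and of it the protocol says "The findings will be used in the statistical analysis to determine the effects on treatment response and safety". In the primary analysis section ApoE4 appears only as an example of a subgroup. Appendix 4 lets the DNA sample be drawn at a later visit and waives it where national law forbids it.

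The sample size (9.7.2) is calculated "using a 2-sample t-test with 90% power at a significance level of 2-sided alpha =0.05", so it credits no covariate.

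**The concern.** The primary comparison looks for a difference of 0.4375 points in an outcome with an assumed SD of 2.05, a standardised effect of about 0.21. Any between-subject variance explained by pre-dose variables shortens the confidence interval. In a linear model with prespecified baseline covariates, this changes neither the treatment difference being estimated nor the type I error. The margin over 90% power is 0.2 percentage points, and section 9.7.3 itself warns that the SD in a trial may exceed the observational one used. With no imputation in the primary analysis and 30% dropout expected, conditioning on more prognostic variables may also make the missing-at-random assumption easier to defend. A covariate list fixed without these variables gives up whatever they could contribute.

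**Working it through.** **Inputs (Protocol 9.7.2).** Placebo mean change and SD "in the placebo group are assumed to be 1.75 and 2.05, respectively"; effect "assuming a 25% reduction in the mean change from baseline CDR-SB at 24 months", so 0.25 × 1.75 = 0.4375; "an estimated 30% dropout rate in this study"; two-sided alpha 0.05; power 90%; 665 per arm.

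**The plan's own figure.** n per arm = 2 × (1.960 + 1.282)² × 2.05² / 0.4375² = 461.4, so 462. Divided by 0.70 this is 660 per arm, 1320 in total. The exact non-central t needs 463 per arm, 1324 in total. The stated 1330 reproduces. With 665 × 0.70 ≈ 465 completers per arm, power by the non-central t is 90.2%.

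**Effect of added covariates.** Replace the SD by 2.05 × √(1 − R²), where R² is the share of month-24 variance the added covariates explain beyond those already in the model. The documents give no such figure, so the range is an assumption. Half-width = 1.96 × SD × √(2/465); equivalent N = 1330/(1 − R²).

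| Assumed R² | SD | Power, 465 per arm | 95% CI half-width | Equivalent N randomised |
|---|---|---|---|---|
| 0 | 2.050 | 90.2% | 0.264 | 1330 |
| 5% | 1.998 | 91.5% | 0.257 | 1400 |
| 10% | 1.945 | 92.9% | 0.250 | 1478 |
| 15% | 1.890 | 94.1% | 0.243 | 1565 |

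**Starting point.** The table applies R² to the marginal SD. If baseline CDR-SB and the strata already explained, say, 10% (assumed), the planned model would have 92.9% power, and a further 10% would raise it to 95.1% (normal approximation). That is a gain of 2.2 points rather than the 2.7 in the table.

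**Larger SD (assumed).** At SD 2.2, power is 85.8%, and 89.1% with R² = 10%. At SD 2.3 it is 82.6%, and 86.3%.

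**Why visit interactions matter.** Take a random-slope illustration with 8 quarterly visits, complete data and an assumed residual SD of 0.8 to 1.0, in which a covariate's effect grows with time. A covariate that explains 5% of month-24 variance through a by-visit term removes only 1.2 to 1.7% if entered with one constant coefficient. For 10%, the constant term removes 2.5 to 3.6%. The same reasoning applies to baseline CDR-SB as now specified.

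**Why a missing-value rule matters.** If subjects lacking a covariate fall out of the model, 5% missing against R² = 5% returns power to 90.2%, and 10% missing lowers it to 88.6%.

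**Parameters.** Age, ADAS-cog14 and FAQ need one column each and a three-level ApoE4 factor needs two. Five columns × 8 post-baseline CDR visits to month 24 (Table 3) = 40. A by-visit term for baseline CDR-SB adds 7.

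**The case against.** The strongest reply is that nothing here is wrong. The model contains the baseline value of the outcome and every stratification factor, and the promised power is reached by an unadjusted calculation. A remark that precision could be better fits almost any trial. That stands, and it sets the weight of the point.

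Several stronger readings are tempting but are not supported:

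- **That the protocol itself calls these variables prognostic.** Section 9.2.3 says of FAQ that it reflects "functional state and should correlate well with AD progression". This justifies FAQ as an outcome; it does not say that baseline FAQ predicts later decline. The same section prefers the 14-item ADAS-cog for its sensitivity in milder disease. The ApoE statements in 9.2.4 and 9.5.1.4.2 concern differences in treatment response, which is effect modification. Neither rationale section names age.
- **That baseline CDR-SB is a weak predictor because entry requires a global CDR of 0.5.** No figure in the protocol shows this. The entry rules on MMSE, CDR and the shopping-list task also narrow ADAS-cog14 and FAQ indirectly. Both overlap with CDR-SB and staging, so only their increment counts.
- **That the change costs nothing.** It needs a rule for missing covariates. Membership of the full analysis set depends only on CDR-SB data, so a subject without baseline ADAS-cog14 or FAQ could otherwise be lost from the primary analysis.
- **That all four are certain to be in hand before dosing.** For ApoE4, Appendix 4 allows otherwise. A late sample does no statistical harm, because genotype does not change; an absent one needs handling.

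What the reply does not remove is that the list is fixed in the protocol, the data are collected anyway, and each practical gap closes with a sentence.

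**Conclusion.** The point holds as a cheap improvement, not as an error, a bias or a shortfall in power. The primary model as written is valid and reaches its stated 90%. Adding the four covariates would give, at 465 completers per arm, power between 90.2% and about 94.1% and a half-width between 0.264 and 0.243 points.

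That range rests on a partial R² of 0 to 15% that is assumed, on the marginal SD of 2.05, on by-visit covariate terms and on no subject being lost for a missing covariate. At R² = 0 there is no gain, and the harm is negligible. The size of the benefit is therefore uncertain; its direction is not in doubt in a trial of this size.

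**What to change.** In 9.7.1.6.1 and the synopsis, before any unblinded look:

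1. Add age, baseline ADAS-cog14, baseline FAQ and ApoE4 carrier status (carrier, non-carrier, not available) to the primary MMRM, each with a visit interaction.
2. Give baseline CDR-SB a visit interaction as well.
3. State that a missing baseline ADAS-cog14 or FAQ is imputed by a simple rule that ignores treatment, for example the mean of all observed baseline values, so that no subject in the full analysis set is dropped.
4. Use the same list in the CDR-SB secondary models (change at 27 months, and the slope model with assessment time in place of visit).

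If blinded or external data can supply a partial R², state the expected gain. The cost is wording, about 40 additional parameters (47 counting the by-visit term for baseline CDR-SB) against roughly 930 completers, and the missing-covariate rule. No assessment, visit or subject is added.
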